To schedule DSMB teleconferences, the program manager will send a Doodle poll to all required attendees: Coordinating Center and sub-site PIs, [name], NIA Program, DSMB Chair and members, as well as DSMB members' assistants if needed (with the DSMB members cc'd in the initial scheduling email). Try to schedule at least 3 months out, as required staff tend to be very busy and often in different time zones. Either [name] or [name] from NIA must be on the call.

Contact information:

Chair of DSMB [name] [contact] Hackensack Meridian Health [name] Assistant: [name] [contact] [name]: [contact] [name]: [contact]	DSMB Member [name] [contact] Cleveland Clinic Las Vegas, NV [contact] Assistant: [name] [contact] [contact]	DSMB Member [name] [contact] University of Alabama Birmingham, AL [contact] Assistant: [name], [contact] [contact]
D1. Sman. [contact]		

The study team is responsible for compiling a blinded report prior to each DSMB teleconference. This report needs to be approved by [name] and submitted to [name] at least 2 weeks before the scheduled teleconference. This report will include:

1. Project Summary

- a. *Major Activities*: This section lists all IRB-approved changes to the protocol since the previous teleconference.
- b. Subject Recruitment: This section contains the number of subjects screened and recruited, as well as demographic information about recruited subjects.
- **2. Serious Adverse Events**: Each SAE report must be included in its entirety, including any information from follow-up correspondence with the IRB after the initial report.
- 3. Patient Flow Charts
- 4. Recruitment Rate by Month
- 5. Baseline Demographic and Clinical Summary Statistics: This section is completed by [name] from the database.

6. Unblinded DSMB report. [name] generates the unblinded report directly to DSMB members with participant data by treatment assignment. Blinded study staff are not privy to this information.

DSMB Communications

All key communications (including protocols, manual of procedures, reports, recommendations and other study-related correspondence) will be distributed by [name] and/or the data management team led by [name] to DSMB board members and NIA program officials.

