- A. The ADCS-ADL must be done by the study physician who sees the patient (At BAI, neuropsych and rating scales are completed per site standard with trained staff and raters). It should be done at the end of the visit, i.e., after NACC and other forms are administered (specific forms will vary from visit to visit but ADCS-ADL should always be done at the end). The ADCS-ADL should be administered to the informant but when the informant is not sure about the answer to a question, it can be done with the patient as well. The study physician must fill it out completely based on the best information available, even if it seems to be spotty based on unclear patient and informant responses.
- B. We will use our own discretion in deciding whether subjects and caregivers should be compensated with Petty Cash, or through filling out a reimbursement form, which would result in a check being sent to the subject or caregiver's place of residence. Reimbursement forms require collection of social security number and W9 completion from the payee.
- C. The RC must do the maximum, not the minimum, and know every detail about their patient(s) to truly make this a successful study. There needs to be an ongoing conversation about patient concerns, not just facts of the study. The single most important thing will be establishing a decent rapport with the study patient and making sure they (as well as their caregivers) know that we're here to address their concerns and make participation in the study convenient for them. This will keep them coming back.

Weeks 2 & 4 Phone Call/Visit

- In-office or telephone call by study physician to assess subject study drug compliance and any patient history changes. This telephone call or in office visit should last approximately 10 minutes.
- Physician will write note and RC will complete medication compliance form.

Medication Compliance Calls: The RC will call the patients or caregivers **once a month** and medication compliance will be documented on a log upon query. These calls will occur throughout the subject's 78 weeks of protocol participation. During phone contacts, patients should be reminded that they will be followed by a physician here. Patients should know exactly what they'll be getting through participating in research.

The following compliand	ce script will be used when pla	cing these calls:
Hi Mr./Mrs.	. This is	calling from Columbia about the "Antiviral
		mily member is enrolled in. Do you have a few minutes

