- For patients consenting to the LP, CSF (and plasma) will be collected ([name] performs the LP, NYSPI RC processes and stores specimens for both NYU and NYSPI LP subjects). The NYSPI RC will fill out the LP and Plasma forms and tubes according to the LP procedure section of this manual. The form/tubes will be checked by the RC, the back-up RC and the program manager.
- Before the patient leaves, the RC will double check that the study physician completed all necessary
 forms. After verification is complete, the coordinator will confirm that all RC forms have been
 completed, as well. The RC must check the checklist for the visit, and ensure that all forms listed in it are
 completed and ticked off on the checklist page. Only after both of these checks have taken place can the
 patient and caregiver be sent home.

Week 26 Visit

The week 26 visit is estimated to take about 2-3 hours.

- Neuropsychiatric measures: MMSE and ADAS-Cog11 (RC at NYSPI, delegated/certified staff at NYU and BAI).
- Clinical assessment: Progress note, CDR, ADCS-ADL, and CIBIC-plus (study physician completes at NYSPI; PI or delegated/certified Sub-I at NYU and BAI).
- SMAC blood chemistry (red top) will be collected to assess kidney function (RC completes). The RC will fill out the NKI requisition (NYSPI) or NYU Langone Lab req if NYU subject, BAI specific lab req if BAI subject; as described in the blood draw policy section of this manual. The req and tubes will be checked by the RC who filled them out, the back-up RC and the program manager. Those who check will be looking to make sure the patients name, X number (med rec number), sex, ward unit, facility name, date and time of draw and order, and proper boxes are checked on the form and match the information on the tubes.
- Coordinator will record vital signs.

• Before the patient leaves, the RC will double check that the study physician completed all necessary forms. After verification is complete, the coordinator will confirm that all RC forms have been completed, as well. The RC must check the checklist for the visit and ensure that all forms listed in it are completed and ticked off on the checklist page. Only after both of these checks have taken place can the patient and caregiver be sent home.

Week 52 Visit

This visit will take 3-4 hours.

- Re-evaluation of diagnosis, Progress note, CDR, ADCS-ADL, CIBIC-plus, and NACC packet (study physician completes at NYSPI; PI or delegated/certified Sub-I at NYU and BAI).

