- The RC will fill out the NKI requisition (NYSPI) or NYU Langone Lab requisition if NYU subject or BAI specific lab req if BAI subject, as described in the blood draw policy section of this manual. The requisition and tubes will be checked by the RC who filled them out, the back-up RC and the program manager. Those who check will be looking to make sure the patients name, X number (med rec number), sex, ward unit, facility name, date and time of draw and order, and proper boxes are checked on the form and match the information on the tubes.
- Re-evaluation of diagnosis, Progress note, CDR, ADCS-ADL, CIBIC-plus, NACC packet, and concomitant medications log. (Study physician completes at NYSPI; PI or delegated/certified Sub-I at NYU and BAI).
- ADAS-Cog11, NACC neuropsychological battery, UPSIT, and vital signs. (RC completes at NYSPI, delegated/certified staff at NYU and BAI).

- Plasma acyclovir specimens, collected from all subjects, should be checked for: ID, draw time, date, date/time of most recent dose, valacyclovir/placebo, DOB, [name], IRB #.
- Patients will have a final MRI and PET Scans, following the protocol of the baseline visit.
- Patients who agreed to the LP will have a third and final LP, providing plasma and CSF specimens.
- Adverse Events will be recorded on the Adverse Events Log (RC completes).
- Medications will be recorded on the Concomitant Medications Log (Study physician completes).
- A Protocol Exit form is completed (RC completes).

Whenever a patient ends the protocol, regardless of time-point, the protocol exit form needs to be completed. If a patient terminates the protocol early for any reason, the patient needs to be brought back to complete all planned study visits and procedures under the intent-to-treat principle. Any intervening treatments or other changes will be documented but will not affect the assessments. During this time, the patient should be instructed not to participate in any other treatment research protocol. Before the patient is free to go the RC should double check that the study physician has completed all necessary forms. After this is checked the coordinator should confirm that all RC forms have been completed. Only after both of these checks have taken place can the patient and caregiver be sent home.

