Study records (scan reports, lab results) for patients referred to VALAD by DPO Providers, will be dropped off in a manila folder, with [name] on NI3. These records will be dispersed to respective DPO provider. RC should compose a brief narrative of what exactly each manila folder contains, and which study visits have been completed to date.

Biological Specimens and Scans:

We will be collaborating with the following laboratories:

- 1. [name]. University of Alabama at Birmingham CSF Specimens and Plasma Specimens
- **2. [name], Ph.D** University of Pennsylvania CSF Specimens
- **3. [name],** Human Genetics Research Core (HGRC) CUMC CSF Specimens, APOE/DNA Specimens, Plasma Specimens
- 4. Quest Diagnostics (HSV ½ IgG)/ARUP Lab (HSV ½ IgM) HSV1/HSV2 Testing
- 5. Nathan Kline Institute (NKI)

Routine Laboratory Testing

6. NYU Langone Local Hospital Lab

Routine Labs for NYU subjects

7. Banner Health Hospital Laboratory (BAI) Routine Labs for BAI subjects

Lab Results

All lab results need to be reviewed and signed by the study physician promptly after they are received. The physician should initial and date all results and indicate any clinically significant findings.

Blood Draw Policy & Procedures

Test	Tube	Visit	Process
SMAC Folate B12		Screen, Week 12, Week 26, Week 78	 Check off Chem 1, TSH, Folate, Vitamin B12 on NKI requisition form/ NYU Langone Lab Req or BAI Lab Req. Invert 5 times.

	8 mL Serum Sep clot activator Ref # 455071P		 Stand up right for 30 minutes before centrifuge. Centrifuge for 20 minutes Fill entire label on tube (Ward 890, get X number from KIS-EMR or equivalent medical record number from NYU and BAI medical records interface) and make sure it matches requisition form. If the blood was drawn at baseline, check off "New Admission" under "Reason for Test". If the blood was drawn at a follow up visit, check off "Other" and specify the study week. Submit to refrigerator with requisition form to room 4200 (NYSPI). NYU will submit these specimens to their lab or lab drop off site, as will BAI. RC's and PM will check tubes and forms and confirm their accuracy.

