[name], MD

[name], University of Pennsylvania Medical Center [name]

Notify UAB Antiviral pharmacology lab [contact], [contact]) when shipment leaves with FedEx air bill number. [contact] ([name] cell phone). Date and time. direct sig

Ship all samples with this form to:

[name]., Antiviral Laboratory Director

Lab Contact: [name], B.S.

University of Alabama at Birmingham Division of Clinical Pharmacology [name]

CSF Storage & shipment: HGRC

- 1. HGRC vials will not be stored on site, they will be dropped off at the HGRC on the day of the LP. The CSF for the HGRC will NOT be frozen, the specimens are dropped off at the HGRC same day of the LP, so freezing isn't necessary.
- 2. There should be four copies of each barcode number on separate stickers. A small sticker should be placed on each of the two cryovials, another (larger sticker) should be placed on the bio sample form, and the last (larger sticker) should be placed on the CSF biological storage log in the bio samples binder. Subject ID, PI, Collection date, and IRB protocol number will also be included in the cryovials brought to the HGRC.
- 3. The RC should fill out the CSF Bio Sample form from the HGRC with the information specified, including the matching barcode sticker.
- 4. The RC should make a copy of this form and bring it to the HGRC. HGRC will keep the copy and sign the original. The signed original should then be copied. One copy of the form should be kept in the patient's chart, and the other should be kept in the bio samples binder.

CSF Analysis and Reports: UAB and UPenn

- a. UPenn: On a quarterly basis, tau, ptau, and AB42 will be analyzed and reported for all subjects. Neurofilament Light (NL) will be analyzed and reported on as well. The site will receive report of NL results, but these results will not be shared with subjects. Only baseline CSF analyses of tau, ptau and AB42 will be shared with subjects.
- b. UAB: At Weeks 12 and 78, plasma acyclovir levels will be drawn and analyzed for all subjects. On a quarterly basis, week 12 and 78 plasma acyclovir levels will be reported to the site, but not shared with subjects. This test isn't clinically relevant but is of relevance to the research team as a check on randomization and subject drug compliance.

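### Plasma acyclovir levels, which can reveal treatment arm, are reported quarterly to the site with only subjects excluded; neither document limits them to unblinded staff

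*Protocol*

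**What the plan says.** Protocol, CSF Analysis and Reports: UAB and UPenn, item b, has plasma acyclovir drawn and analysed in every subject at weeks 12 and 78. On reporting it says: "On a quarterly basis, week 12 and 78 plasma acyclovir levels will be reported to the site, but not shared with subjects". It calls the test not clinically relevant, but says that it "is of relevance to the research team as a check on randomization and subject drug compliance".

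Other parts of the protocol bear on this:

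- **Blind.** The Week 78 Visit section keeps the blind until the final subject has completed all week-78 procedures.
- **DSMB report.** For the by-arm report to the Data Safety and Monitoring Board, the restriction is written out: "Blinded study staff are not privy to this information".
- **Code.** The section on Research Pharmacy Ordering Study Drug/Randomization places the randomization code with the research pharmacy and the lead of the Data Coordinating Center (DCC).
- **Laboratory results.** The list of collaborating laboratories opens with "University of Alabama at Birmingham CSF Specimens and Plasma Specimens". Under the separate heading Lab Results, the rule is: "All lab results need to be reviewed and signed by the study physician promptly after they are received".
- **Raters.** The baseline notes, item A, say: "The ADCS-ADL must be done by the study physician who sees the patient", with an exception that lets BAI use trained raters under its own standard. For week 52 the entry is "CDR, ADCS-ADL, CIBIC-plus, and NACC packet (study physician completes at NYSPI; PI or delegated/certified Sub-I at NYU and BAI"; for week 78 it is "CDR, ADCS-ADL, CIBIC-plus, NACC packet, and concomitant medications log. (Study physician completes at NYSPI; PI or delegated/certified Sub-I at NYU and BAI". The ADAS-Cog11 is given by the research coordinator at NYSPI and by delegated staff at NYU and BAI.

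The SAP (section 5) uses the acyclovir concentrations only for a summary by mean and standard deviation.

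**The concern.** The protocol's Background describes valacyclovir as a pro-drug of acyclovir. A measurable plasma level therefore points to the active arm. An undetectable level points to placebo, or to an active-arm participant who is not taking the drug. A list of such levels by subject comes close to a list of allocations.

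The trial is double-blind, and its clinical outcomes are scored by people at the sites. If a rater learns the likely arm, ratings can shift. The exposure is greatest for the ADCS-ADL, the secondary outcome: it is an informant interview, and the physician must complete every item on the best information available, even when the answers are unclear. It is smaller for the primary outcome, the ADAS-Cog11, which is made up of cognitive tests. A reader of the results cannot judge either case, because neither document names the recipients of the levels, the form of the reports or their dates.

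**Working it through.** There is no planned figure to reproduce. The check sets the passages side by side and adds one count of weeks.

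1. **Are the levels subject-level?** Item b does not use the word individual. It does say that samples come from all subjects and serve to check randomization and subject compliance; group means could do neither. The plasma shipped to UAB also travels with logs that carry subject ID, draw time and time of last dose. Subject-level reporting is a reasonable inference, but it remains an inference.

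2. **Who is excluded?** Only subjects. Item a of the same section makes the same contrast for neurofilament light, an ordinary biomarker: the site receives the result and subjects do not. Nothing in item b marks the acyclovir recipient as a different, unblinded function. The stated user is the research team.

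3. **Is access restricted elsewhere?** The DSMB restriction covers the by-arm report only. The pharmacy section names the code holders but does not send them the levels. The blind-break rule is general, and item b does not say how quarterly reporting complies with it. Item b covers plasma only; the routing of CSF acyclovir results is not stated.

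4. **Is there a path to the ADCS-ADL rater?** Read literally, the Lab Results rule covers every result, UAB is among the listed laboratories, and the signing physician rates the ADCS-ADL at NYSPI. The link is weaker at NYU and BAI, where the PI, a delegated sub-investigator or (at BAI) a trained rater may score it. This makes the path possible. It is not a documented routing.

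5. **Is there a path to the ADAS-Cog11 rater?** Coordinators assemble the research chart, which has a laboratory section, but nothing says that acyclovir reports are filed there. Access is possible but not shown.

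6. **Could a level arrive before a rating?** Only the week-12 level matters here.
   - From the draw to week 52: 52 − 12 = 40 weeks. To week 78: 78 − 12 = 66 weeks.
   - Taking a quarter as 13 weeks, a result that just misses a report waits at most 13 weeks for the next one. That leaves 40 − 13 = 27 weeks and 66 − 13 = 53 weeks for shipping and assay.
   - Samples ship in batches of five subjects with no calendar limit, and assay time is not given. A result could therefore arrive before both visits; the documents do not show that it did.

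**The case against.** The strongest defence is that an unblinded recipient was intended. A level cannot check randomization unless it is compared with the code, and the code sits with the pharmacy and the DCC lead. The text says site in the singular in a three-site trial, which could mean the coordinating centre. The rule that keeps the blind to the end of the trial has no exception for laboratory data and need not be repeated in every section. This reading is plausible, but the text does not state it, and naming the research team as the user leaves it open.

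The second defence concerns the sign-off rule. It goes on to ask for clinically significant findings to be marked, which fits clinical laboratory work, whereas item b calls the acyclovir test not clinically relevant. Where the protocol wants a research report signed and filed, as for HSV antibodies, amyloid reads and MRI, it says so; no such step is written for acyclovir. This stands. A reader might infer from the word all that physician raters did receive the levels. The documents do not support that: the route is only possible.

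Third, the visits are over and procedure manuals outside this file are mentioned, so a routing rule may exist elsewhere. This also stands. It makes disclosure the main practical remedy, and it does not remove the gap in the protocol.

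**Conclusion.** The concern holds as a gap in the protection of the blind. As written, item b sends results that can reveal the arm to the site during a double-blind trial, and it excludes only subjects. The conclusion rests on one inference, that the reports are at subject level, and on the protocol's own statement about the pro-drug.

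A reader might go further and infer that outcome raters were unblinded, or that the primary result is compromised. Neither follows. No document shows that any rater saw a level, and the ADAS-Cog11 raters have no documented access. No size of bias can be derived, because recipients, form and reporting lag are all unstated. The point calls for a correction and a disclosure. It is not a reason to discount the primary analysis.

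**What to change.** **Text.** Amend item b so that subject-level plasma and CSF acyclovir results go only to the unblinded pharmacy/DCC function that holds the code, and have that function do the randomization and compliance check. Exempt these results from the physician's sign-off under Lab Results. Release them to site staff, investigators and raters only after the blind is broken. The sentence used for the DSMB report is a suitable model.

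**Reporting.** The SAP is written in the past tense and the visits are complete, so new wording cannot change what happened. State by site who received subject-level levels, in what form and on what dates. If access was restricted in practice, one sentence settles the matter. If any rater had access before rating, state that as a limitation, chiefly for the ADCS-ADL at the visits concerned.

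**Cost.** The text change is one routing sentence with its release condition and one exemption. Sites lose an in-trial compliance readout, but kit checks at visits and monthly compliance calls remain, and the SAP's summary of concentrations is unaffected. The disclosure needs a check of the laboratory's report dates and recipients.

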- 2. RC will schedule patient (or patient and coordinator if NYU patient and NYU coordinator joins for the scan) to meet her/him at the Memory Disorders Clinic 30-45 minutes before scan. NYSPI RC must remain present for all scanning procedures if running an NYU patient. Typically, the PET scan will not be the first thing a patient does at baseline or week 78, for these longer visits RC's should keep their eye on the time to

- ensure that they arrive at the PET center at least 15 minutes before their scan time to check them in at the front desk.
- 3. NYSPI RC needs to bring the Pregnancy Attestation Form, a copy of the PET Requisition, and a copy of the signed consent or consents (NYU and NYSPI) if NYU subject. The PET center will keep all forms. All of these forms can be uploaded to iLab which eliminates the need for a hard copy. If the consent form has been changed between the patient's week 0 visit and week 78 visit the patient must sign the updated consent and the NYU or NYSPI RC should bring this updated consent to week 78 PET scan. Always bring the entire subject chart with you if you feel this will be helpful in answering any question staff might pose. The subject will be asked to state his/her name and DOB, which should match the orders/scan request placed by the PI/coordinator.
- 4. RC needs to bring her/his dosimetry badge.
- 5. When checking in the person at reception will only need the IRB protocol number from the RC. Once the patient is checked in the RC will wait in the PET center with the patient and caregiver until they are called in.
- 6. NYSPI RC will have all forms ready for review however the PET center will likely have the forms printed from the prior iLab submission.
- 7. RC will make sure the patient has removed all metals from head pins, clips, earrings.
- 8. The PET technician will set up the patient on a bed with a blanket for them to relax during the uptake period.
- 9. Once the patient is set up the RC will go to the waiting room to wait for the patient. If the patient does not have a caregiver with them the RC needs to remain in the room with the patient but sit at least 6 feet away. If the caregiver is present, they will remain with the patient until it is time for them to enter the scanner, then come out to the waiting room with the RC.
- 10. Patient will be at the PET center for about 1.5 hours (scan acquisition time is 20 minutes and the uptake time is 50 minutes). The RC will go back to the scanner 5 minutes before the scan time is up to retrieve the patient and sign a copy of the PET checklist.
- 11. Once the scan is done the RC will take the patient and caregiver back to the clinic to complete any other necessary measures or to the most convenient location to exit and head to their train or car, if NYU subject, they may leave at this time.

POST SCAN PROCEDURES:

- 1. Instruct patient that he/she can continue normal activities after PET scan.
- 2. Patient is advised to drink several glasses of water and contact study physician if there is any persisting pain in his/her hand or arm (slight soreness and bruising is expected since a small tube was inserted into vein of arm).

Obtaining Amyloid Scan Reads

(completed through the PET Department's Safety Read System in RedCap):

Amyloid reads will be completed by [name], MD ([contact]) and/or [name], MD ([contact]) Amyloid read reports are available in RedCap 1-10 days following amyloid PET scan.

To access an Amyloid read:

- 1. Website: https://radiosftp.cpmc.columbia.edu /redcap/redcap v8.11.7/DataEntry/record status dashboard.php?pid=31&pagenum=2
- 1. Navigate to "Record Status Dashboard" (on the left-hand side of the home-page) and all VALAD subjects are on the list of study subjects receiving reads that will automatically populate when one navigates to the Record Status Dashboard.
- 2. Subjects are identified on this list by "NYSPI #7537" followed by respective Study ID.
- 3.RCs must download a PDF the report with "saved data," print, file in subject chart and obtain signature and date on the amyloid read by the patient's study MD.

4. SUVR: Once the analysis and decisions about how to interpret SUVR are confirmed by [name], we will decide how to communicate results to subjects and caregivers, with Drs. [name] and [name]. [name] would like to be informed of discrepant cases (between amyloid pos/neg status and SUVR AD Dx interpretation).

Study physicians will review the amyloid read and SUVR results with the patient and caregiver when they come in for their next visit. If the patient wants the results sooner the physician may call to discuss but inperson discussion is strongly preferred. Some reads may require immediate follow up.

- 1. Prior to filing, PI or study physician will need to sign and date at the bottom of the report.
- 2. Reports for NYU subjects will be sent to NYU from NYSPI coordinator via secure email after review by [name]. [name] will call NYU subjects with findings.

18F-MK-6240 Tau PET Imaging Procedures (NYSPI/NYU specific, BAI will follow this protocol with modification made per facility standard) — Week 0 & Week 78

General Note:

- a) For patients who have confirmed radiation exposure from the past year, contact [name] via email for review of patient medical records/self-report of scanning as soon as you've been made aware of the issue. This information is captured on the Metal Screening Questionnaire and the Medical Screening Form.
 Prior research scans will count toward actual, calculated radiation exposure by [name] but SOC scans will not. [name] is to evaluate research scan radiation exposure prior to running PET scans. We should go ahead and book scans under the assumption that there will not be a significant delay in scanning, even for those patients who have had previous research scans; we will cancel/rebook if need be per [name].
- b) For the sake of IRB Compliance, the VALAD team will always email [name] in regard to patients who have been exposed to radiation in the past year (SOC or research). [name] will compose either a stock reply that piggy backs off of [name] decision that SOC scans will not count toward radiation exposure in this protocol, or a more pointed reply with pointed scan scheduling directions if a patient had a research scan(s) in the past year. IRB needs assurance that patients will not exceed 5 REM yearly allowable limit FDA guidelines.

Scheduling:

- 1. NYSPI Coordinator uses their own iLab account to fill out time request form. Each participant will need a separate request (if there are 3 participants, 3 separate requests will need to be initiated). NYU staff will communicate subject availability and relevant forms to NYSPI coordinator within 1 day of successful screen being confirmed.
- 2. NYSPI Coordinator will create an order for the PET scan in EPIC, in tandem with iLab.
- 3. Confirm if available dates work with subject's schedule/follow-up with potential dates.
- 4. Coordinator officially requests slot. Please note slots are first-come-first-serve. It is best to try to schedule as far in advance as you can per protocol.
- 5. Coordinators will need to attach all the necessary forms including a scanned copy of the signed consent form, the scan requisition form, and the pregnancy attestation form.

Please Note the following tau PET Scheduling Proclivities:

Scheduling for MK-6240 will utilize the following time slots. We allow two tau dose synthesis failures before proceeding with randomization.

- 1. MK-6240 injection times will be concentrated on Monday's and Friday's.
- 2. MK-6240 will not be available on Tuesdays, Wednesdays, and Thursdays.
- 3. The following injection times are available Monday's and Friday's: 14:00, 14:15, 14:30, 15:30, 15:45, and 16:00
- 4. The PET scan requisition form can be downloaded directly in iLab or from the server. Note that there are separate forms for amyloid and tau scans.
 - a. The date needs to the filled out in 01-Jan-2020 format. The scan requisition section needs to be digitally signed with a PDF editor.

- b. Use military time when filling out the time request form. Military time will be calculated in 24 hours. 12.00 am would be 0000 hours 12 pm would be 1200 hours and 11 pm would be 23 hours.
- 5. Pregnancy: All female patients need to be sign prior to scheduling their appointment. The patient will also need to indicate the year of their last menstrual period.
 - a. You may want to contact [name] ([contact]) regarding this process, she can also answer questions regarding the cancellation policy.

PET PRE-SCAN PROCEDURES:

- 1. During study screening:
 - a. check for inability to cooperate/claustrophobia (sedation is not offered for this protocol), inability to lie on scanner bed for 40 minutes, inability to achieve venous access sufficient for tracer administration, and past radiation exposure.
 - b. Complete pregnancy form if appicable
- 2. Schedule scan 2-3 weeks in advance in iLab. Scans need to be cancelled 48 hours in advance, otherwise we will be charged for the scan time. Call patient and caregiver 10 days and 5 days before scan to confirm appointment. NYU staff must place these reminder calls to their subjects.
 - a. If they do not pick up, leave voicemail for them to call back to confirm.
 - b. If patient and caregiver do not confirm/do not pick up the phone cancel PET scan.
- 3. Call patient and caregiver 3 days and 1 day before scan to remind them of appointment.

ON THE DAY OF THE SCAN:

- 1. Patient should eat breakfast and take all of their medications, as usual, prior to arrival at PET Center (RC will inform them at 24-hour confirmation). If a patient has a long schedule for that day, the patient should bring all medications that they need to take e.g., medications typically taken during lunchtime if scans are scheduled before and after lunchtime.
- 2. NYSPI RC will schedule patient (or patient and coordinator if NYU patient) to meet her/him at the Memory Disorders Clinic 30 minutes before scan. NYSPI RC must be present for all scanning procedures if running an NYU patient. NYU RC's presence is optional. Typically, the PET scan will not be the first procedure a patient completes at baseline or week 78, for these longer visits RC's should keep their eye on the time to ensure that they arrive at the PET Center at least 15 minutes before their scan time to check in at the front desk.
- 3. NYSPI RC needs to bring the Pregnancy Attestation Form, a copy of the PET Center Checklist, and a copy of the signed consent or consents (NYU and NYSPI) if NYU subject. The PET center will keep all forms. If the consent form has been changed between the patient's week 0 visit and week 78 visit, the patient must sign the updated consent and the RC should bring this updated consent to week 78 PET scan. Always bring the entire chart with you. This will be helpful in answering any question staff might pose.
- 4. RC needs to bring her/his dosimetry badge.
- 5. When checking in at reception, the RC will need the IRB protocol number. Once the patient is checked in the RC will wait at the PET center with the patient and caregiver until they are called in.
- 6. NYSPI RC will give the consent form, and pregnancy attestation, subject ID, and RPO forms to the PET tech.
- 7. RC will make sure the patient has removed all metals from head pins, clips, earrings.
- 8. Pre-injection vital signs (BP, heart rate, temperature, respirations) must be collected by the PET tech and recorded on the PET Center Checklist. The RC must check to ensure this has been done.
- 9. RC(s) will remain with patient and caregiver during the injection process. RC and caregiver must sit or stand at least 6 feet away from the patient at all times to reduce exposure to radiation. The PET technician will set the patient up on a wheeling bed with a blanket during the uptake period. At this time, the caregiver should go and wait in the PET center waiting room unless the subject is anxious and needs the caregiver in room with them.
- 10. The RC should remain with the patient and use this time to organize the patient's chart and if the patient is in condition for measure administration, administer measures as required per protocol. Best use should be

- made of the lengthy wait time for radioligand uptake. The RC should always be 6 feet away from the patient.
- 11. Patient will be at the PET Center for 2 hours (scan acquisition time is 40 minutes and the uptake time is 80; 120 minutes in total). The RC (s) will go back to the scanner 5 minutes before the scan time is up to retrieve the patient and review/sign a copy of the PET checklist.
- 12. Post scan vital signs (BP, heart rate, temperature, respirations) must be collected on the PET center checklist, this will have to be checked by an RC every time an 18F-MK-6240 scan is completed.
- 13. Room # and Scanner Type (ID) will need to be recorded on the PET center checklist and tracked per patient from baseline to 78 weeks to ensure consistency of scanner used.
- 14. Once the scan is complete the RC will take the patient and caregiver back to the clinic to complete any other necessary measures. NYU subjects and coordinators may leave at this time.

POST SCAN PROCEDURES:

- 1. Instruct patient that he/she can continue normal activities after PET scan.
- 2. Patient is advised to drink several glasses of water and contact study physician if there is any persisting pain in his/her hand or arm (slight soreness and bruising is expected since a small tube was inserted into vein of arm).
- 3. 24 hours after the scan, the RC will place a follow up safety call to the patient or caregiver to assess for adverse events and/or pain. RCs will call respective subjects.
- 4. Clinical reads will never be performed on tau scans. Performing clinical reads with non-FDA approved tracers is against federal regulations.

Important Reminder for RCs:

[name] has advised of the following policy: if tau imaging procedures get canceled due to technical issues, the main goal is to keep the patient in the protocol. Therefore, the patient may not complete an imaging procedure, but continue in the protocol.

If a patient is unwilling to do the tau PET scan, the patient will still be enrolled in the protocol and will be followed to 78 weeks. This will be a protocol deviation. Of course, this is only a final resort, and all decisions must be reviewed with the patient's study physician and [name], if needed.

Important Contact info for PET:

[name] (Director of PET Center Technical Services): [contact]; [contact] **[name] (Project Coordinator)**; [contact]; **[contact]** [name] (PET Center Director/Attending Radiologist): ([contact]) [name] (Attending Radiologist): ([contact])

MRI Protocol: NYSPI MRI Suite (BAI will follow this protocol with modification made per site standard)

MRI PRE SCAN PROCEDURES: - Week 0 & Week 78

- 1. After Recruitment and screening complete the Metal Screening Questionnaire. All implants NEED TO BE CONFIRMED and reviewed with the MRI suite in tandem with the Metal Screening Questionnaire.
 - ** Obtaining MRI Clearance** If the patient checks 'YES' for any item on this questionnaire (examples include metal stents, wire mesh), clearance must be obtained prior to the MRI scan or the scan will not take place. It is acceptable to schedule the scan prior to obtaining clearance. The coordinator must obtain the name of the patient's implanting surgeon from the patient/caregiver as soon as possible. It is the coordinator's responsibility to follow-up with the patient and/or surgeon to determine the presence or absence of a contraindication. The coordinator will then fax/email the surgeon's office the MRI suite's Request for Proof of MR-Safe Implants, including a signed Release of Information and a fax cover sheet with the patient's name, DOB, and any other available information

about their surgery. This form must be completed and signed by the surgeon. The coordinator will email the completed form to [name] ([contact]) for clearance. The coordinator should print a hard copy of the Metal Screening Form, Request for Proof of MR-Safe Implants, and [name] clearance email to bring to the scan. If requested by [name], the subject should be advised that there is a possibility of movement and overheating of the implant as a result of the scan.

